 - c. Informed consent available in either English or Malay language (See Appendix 2) will be obtained prior to enrollment into the study. The consent will be taken by the principal investigator at time of admission in Sibug Hospital Labour Ward.
 - d. A data collection form will be filled up and details including personal information will be obtained (Appendix 3).
 - e. Eligible subjects will be randomly assigned to one of the treatment groups below.
 - i. Group 1: IOL with membranes sweeping
 - ii. Group 2: IOL with transcervical Foley catheter
 - f. Blocked randomisation, in a block size of 6 and an allocation ratio of 1:1, will be performed using a computer-generated randomisation sequence by Research Randomizer (available online at <https://www.randomizer.org/>). The allocation assignment indicating “membrane sweeping” or “transcervical Foley catheter” will be sealed in sequentially numbered, opaque envelopes by principal investigator, . Envelopes will be kept in a locked box in Labour Ward. When study consent is signed, the next sequential envelope will be taken out from the box and opened to determine allocation.

- g. This is a non-blinded study in which subjects, medical staffs, and investigators are not blinded to group assignment. This is because both IOL methods are distinctly different procedure. However, both intervention arms are considered receiving equal treatment. In term of safety, both membrane sweeping and transcervical Foley catheter are non-pharmacological in nature and thus the risk of scar rupture does not differ in both methods. In term of efficacy, there is no previous study to compare effectiveness between these two methods. Individual studies revealed that membrane sweeping is likely to reduce the need for formal IOL in post-date pregnancy and transcervical Foley catheter could improve cervical favourability.
- h. IOL will be done on the next morning. Pre-induction cardiotocograph (CTG) will be performed to ensure normal fetal heart rate prior to IOL.
- i. In Group 1, membrane sweeping involves the insertion of a digit past the internal cervical os followed by three circumferential passes of the digit causing separation of the membranes from the lower uterine segment. When the cervix is closed, a massage of the cervical surface for 15 to 30 seconds will be performed instead. Membrane sweeping will be undertaken twice a day at 8 to 10 hours apart.

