 - i. Subjects may withdraw voluntarily from study at any time upon their request.
 - ii. Subjects are inappropriately enrolled without fulfilling inclusion/exclusion criteria.
 - iii. Subjects develop spontaneous labour before IOL procedure is undertaken.
- b. Follow up process:
 - i. The withdrawn subjects will be managed according to local protocol under Department O&G, Sibu Hospital.
 - ii. The withdrawn subjects data will be destroyed as it will not be used for data analysis.
- c. The withdrawn subjects will be replaced with new subjects in order to meet the required sample size.

TREATMENT AND PROCEDURES

1. Treatment and medications that are permitted during the trial:
 - a. Amniotomy
 - b. Oxytocin augmentation when contractions are not optimised
 - c. Abdominal and vaginal examination to assess labour progress
 - d. Intrapartum continuous fetal heart rate monitoring
 - e. Fetal scalp sampling in the presence of non-reassuring fetal heart rate
 - f. Instrumental delivery or emergency Caesarean section if indicated

2. Both IOL methods of membrane sweeping and transcervical Foley catheter do not contain drug or medication. Thus, the risk of uterine rupture is similar to spontaneous labour in women with previous Caesarean delivery. If scar dehiscence is highly suspected during labour, standard management with recourse to emergency Caesarean section will be undertaken.

3. Treatment and medications that are not permitted during the trial:
 - a. Vaginal prostaglandin E2

ASSESSMENT OF EFFICACY

1. Primary outcome:
 - a. Overall induction to delivery interval.
2. Secondary outcomes:
 - a. Induction outcomes:
 - i. Improvement of modified Bishop score at interval of 24 hours and 48 hours after induction.
 - ii. Whether oxytocin augmentation is required.
 - b. Delivery outcomes:
 - i. Mode of delivery.
 - ii. Duration of oxytocin augmentation overall and in vaginal delivery group.
 - iii. Induction to vaginal delivery interval.

- iv. Amniotomy to vaginal delivery interval.
- v. Vaginal delivery rate within 24 hours of induction and between 24-48 hours of induction.
- c. Maternal outcomes:
 - vi. Uterine hyperstimulation (> 5 contractions per 10 minutes for at least 20 minutes or a contraction lasting at least 2 minutes with/without abnormal fetal heart rate).
 - vii. Uterine rupture.
 - viii. Post-partum haemorrhage (estimated blood loss \geq 500 ml).
 - ix. Maternal pyrexia (temperature >38.0 °C once, or 37.5 °C on two occasions 2 hours apart).

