 - x. Duration of hospitalisation.
- d. Neonatal outcomes:
 - i. APGAR score at 5 minutes.
 - ii. Cord pH.

ASSESSMENT OF SAFETY

1. No adverse events (AEs) will be expected during the course of study because there is no involvement of pharmacological drug or product. Both methods of membrane sweeping and transcervical Foley catheter do not contain drug or medication. Thus, the risk of uterine rupture is similar to spontaneous labour in women with previous Caesarean delivery. However, maternal discomfort and vaginal bleeding following membrane sweeping and unknown latex allergy following transcervical Foley catheter insertion may occur, and subjects will be informed of this risk in the informed consent.
2. All other invasive (amniotomy, fetal scalp sampling in the presence of non-reassuring fetal heart rate, instrumental delivery or emergency Caesarean section if indicated) and non-invasive procedures (maternal vital signs observation and intrapartum continuous fetal heart rate monitoring) and evaluations (abdominal and vaginal examination to assess labour progress) included in this protocol are considered to be standard of care in evaluation and management of women with one previous Caesarean delivery undergoing IOL and would have been performed as part of routine practice.

3. Report of adverse events eg. SAEs, SUSARs.
 - a. When adverse event of any type occurs, local SAE/SUSAR report will be created by principal investigator and notified via SAE Platform on NMRR website.
 - b. Subjects who experience SAE/SUSAR will be followed up by principal investigator and a follow up report will be submitted.
 - c. For “Non-life threatening SUSARs” eg. latex allergy associated with Foley catheter insertion, vasovagal attack following membrane sweeping, and cervical tear, initial report is to be submitted within 15 calendar days followed by a follow up report.
 - d. For “Life threatening SUSARs” eg. uterine rupture and maternal sepsis, initial report is to be submitted within 7 calendar days followed by a follow up report within the next 8 calendar days.

4. Process and duration of follow-up of adverse events
 - a. Latex allergy associated with Foley catheter insertion
 - i. Foley catheter will be removed immediately.
 - ii. Steroids and anti-histamine will be administered as rescue medication.
 - iii. Closed monitoring of vital signs and oxygen saturation for 24 hours.
 - b. Vasovagal attack following membrane sweeping

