 - i. No further membrane sweeping will be performed.
 - ii. Affected subject will be withdrawn from the study.
 - iii. No rescue medication is needed as condition is self-limiting.
 - iv. Closed monitoring of vital signs and oxygen saturation for 24 hours.
 - c. Cervical tear
 - i. Examination under anaesthesia will be performed immediately.
 - ii. Cervical repair will be performed.
 - iii. Subject will be followed up till 42 days post-delivery (completion of puerperal period).
 - d. Uterine rupture
 - i. Emergency laparotomy will be performed immediately.
 - ii. Depend on the severity of uterine rupture, uterine repair or hysterectomy may be warranted.

- iii. Subject will be followed up till 42 days post-delivery (completion of puerperal period).
 - e. Maternal sepsis
 - i. Blood culture and high vaginal swab for culture will be taken.
 - ii. Broad spectrum antibiotics will be started as rescue medication.
 - iii. Unstable subjects will be nursed in intensive care unit.
 - iv. Subject will be followed up till 42 days post-delivery (completion of puerperal period).
5. Compensation of adverse events
- a. In the event of a bodily injury or illness directly resulting from the membrane sweeping or transcervical Foley catheter insertion, the department will pay for reasonable and necessary treatment.
 - b. The department is not responsible for medical expenses due to pre-existing medical conditions, any underlying diseases, any ongoing treatment process, subjects' negligence or willful misconduct, the negligence or willful misconduct of the investigators or the study site or any third parties.

STATISTICS

1. All results will be analysed using the Statistical Package for Social Sciences for Windows (SPSS for Windows).
2. Normality of numerical data (Bishop score, induction to delivery interval, induction to vaginal delivery interval, amniotomy to vaginal delivery interval, duration of oxytocin augmentation, duration of hospitalisation, APGAR score at 5 minutes, cord pH, neonatal birth weight) will be assessed using Kolmogorov-Smirnov analysis. Independent T-test (data with normal distribution) or Mann-Whitney U test (if data not normally distributed) will be used to compare these outcomes between the group of membrane sweeping and group of transcervical Foley catheter.
3. Chi-square test will be used to compare:

- a. The requirement of oxytocin augmentation following induction between the group of membrane sweeping and group of transcervical Foley catheter.

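### Women withdrawn after randomisation are dropped and their study data destroyed, with one withdrawal rule listed for sweeping only, so the groups are not analysed as randomised

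*Combined protocol and SAP*

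**What the plan says.** **Timing and blinding (Trial Design, 5.f to 5.h).** Consent is taken at admission. "When study consent is signed, the next sequential envelope will be taken out from the box and opened to determine allocation". Induction is done the next morning. "This is a non-blinded study in which subjects, medical staffs, and investigators are not blinded to group assignment".

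**Withdrawal (Selection and Withdrawal of Subjects, 6).** There are three criteria. The first is "Subjects may withdraw voluntarily from study at any time upon their request". The others are enrolment in error and spontaneous labour before the procedure. For all of them, "The withdrawn subjects data will be destroyed as it will not be used for data analysis" (6.b.ii), and 6.c replaces them with new subjects.

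**Adverse events (Assessment of Safety, 4).** Item 4.b concerns "vasovagal attack following membrane sweeping", and 4.b.ii adds "Affected subject will be withdrawn from the study". Item 4.a, latex allergy with the Foley catheter, says "Foley catheter will be removed immediately" and lists rescue medication and monitoring, with no withdrawal from the study. Cervical tear, uterine rupture and maternal sepsis are followed to 42 days after delivery.

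**Analysis (Statistics, 2).** The t-test or Mann-Whitney test "will be used to compare these outcomes between the group of membrane sweeping and group of transcervical Foley catheter". Neither this item nor the rest of the section says which women make up those groups.

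**The concern.** Randomisation makes the arms comparable only if the women randomised are the women analysed. Here the plan removes some of them because of what happens later, in a trial where each woman knows her method.

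Both routes out after the start of the procedure can depend on arm and on outcome. A woman may leave because of discomfort, or because her induction is slow. The vasovagal rule acts in one arm by construction. If the women removed would have had longer or shorter induction-to-delivery intervals than those who stay, the primary comparison is shifted.

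Destroying the data makes this irreversible. Nobody could later run an intention-to-treat or sensitivity analysis from the study dataset, or describe who was lost.

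The satisfaction objective (Objectives, 2.e) is exposed as well. The data form (Appendix 3, Section D) asks whether the woman would take part again. Women who left are plausibly the most likely to say no, and their answers are not counted.

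**Working it through.** **1. Which losses come after randomisation?** The envelope is opened at consent and the procedure follows the next morning, so all three withdrawal criteria and the vasovagal rule operate after allocation.

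| Route | When | Can it depend on arm? |
|---|---|---|
| Voluntary (6.a.i) | Any time, including after the procedure | Yes: the woman knows her method |
| Vasovagal attack (Safety 4.b.ii) | After sweeping | Yes: listed for sweeping only |
| Enrolled in error (6.a.ii) | After allocation | Possibly: judged unblinded |
| Labour before the procedure (6.a.iii) | Before any treatment | Probably near neutral |

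The last row is a lesser point. No treatment has been given, and the primary interval as worded has no starting point for these women.

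**2. Is the vasovagal case a data exclusion?** It is not among the three criteria in 6.a. It becomes one when 4.b.ii, which withdraws the woman from the study, is read with 6.b.ii, which destroys the data of withdrawn women. No text exempts it. Of the five listed adverse events, it is the only one with a withdrawal instruction.

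**3. Who is retained?** Expelled catheters and failed inductions stay in (Trial Design, 5.j and 5.s), and Appendix 3 records the interval whatever the mode of delivery. The problem is confined to withdrawn women. Replacement is not itself a source of bias, but it duplicates the 15% dropout allowance in the sample size section (4.c).

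**4. How large could the bias be?** The plan gives no SD, target difference, final sample size or withdrawal rate by arm, so there is no stated figure to reproduce. What follows is an illustration on assumptions.

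*Sample size.* The plan's formula is n = 1 + 2C(s/d)². With two-sided alpha 0.05 (sidedness is not stated) and power 0.80, C = (1.960 + 0.842)² = 7.849. Assuming a target difference of half an SD, n = 1 + 2 × 7.849 × 4 = 63.8, so 64 per arm analysed. With the 15% allowance, 64 / 0.85 = 75.3, so 76 per arm.

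*Bias.* Let w be the share lost, in one arm only, and D the difference in mean interval between lost and retained women, in SDs. The arm mean shifts by w × D.

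*Type I error* = P(|Z + w × D × √(n/2)| > 1.96). For w = 0.05, D = 1 and n = 64, the shift is 0.05 × √32 = 0.283, which gives 0.059.

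| Share lost, one arm | D (SD) | n = 40 | n = 64 | n = 100 |
|---|---|---|---|---|
| 2% | 0.5 | 5.0% | 5.0% | 5.1% |
| 3% | 1 | 5.2% | 5.3% | 5.5% |
| 5% | 1 | 5.6% | 5.9% | 6.4% |
| 10% | 0.5 | 5.6% | 5.9% | 6.4% |
| 10% | 1 | 7.3% | 8.7% | 10.9% |
| 15% | 1 | 10.3% | 13.6% | 18.6% |

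A t-test simulation with 40,000 runs at 64 per arm gave 5.9% for 5% lost at 1 SD and 13.6% for 15% at 1 SD, in agreement. Balanced loss of similar women leaves the error at 5.0%. The 15% row is an upper case: it borrows the plan's overall dropout allowance and places all of it in one arm.

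In the interim sample of 12 per group, one withdrawal is 1/12 = 8.3% of an arm.

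**The case against.** The best case against is about size.

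- **Rarity.** The vasovagal rule concerns an event for which the plan gives no rate, and the safety section expects no adverse events. Voluntary withdrawal is open to both arms equally, and follow-up runs only from induction to delivery, so there is little time to leave. Nothing in the documents shows that lost women would differ by 0.5 to 1 SD. This stands: no material distortion can be demonstrated, and the larger figures above are not forecasts.
- **Data survive elsewhere.** Hospital records are kept, study data are stored for 5 years (Confidentiality, 4), and a vasovagal attack is listed for safety reporting with a follow-up report (Safety, 3). These passages conflict with destruction, but they do not cure it, because no provision brings hospital records back into the analysis for withdrawn women. The passages must be reconciled.
- **Respect for participants.** Destruction may have been promised at consent. The consent text is not available here, so this cannot be checked. However, the rule also covers women withdrawn by the investigators, and the reason it gives is that the data will not be analysed, not privacy.
- **Satisfaction.** It is an objective but does not appear in the outcome list, the Statistics section or the dummy tables, and a woman who leaves may never complete the form. Keeping her data would not necessarily recover her answer. This stands, and the point is secondary.

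**Conclusion.** The concern holds and should be fixed before the trial runs. The plan does more than leave the analysis population undefined: it states a rule that removes randomised women for reasons arising after allocation, one of them listed for a single arm, and nothing in the Statistics section overrides it.

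Confidence is high on the text. The size and direction of the bias are unknown. With few losses the effect on type I error would be negligible, and only heavy, one-sided loss of women with very different intervals would be serious. The case for change rests on principle and irreversibility: losses can depend on arm and outcome in an unblinded trial, and once the data are destroyed nobody can show that they did not. It assumes that withdrawal from the study means the same thing in the safety section as in the withdrawal section.

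**What to change.** 1. **Randomise later.** Open the envelope the next morning, after the pre-induction CTG and after confirming that the woman is still eligible and not in labour. This removes nearly all losses from early labour and allows an eligibility recheck. It does not address the two routes after the procedure; item 2 does.

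2. **Replace 6.b.ii and 6.c** with wording to this effect:

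> All randomised women are analysed in their allocated group. Data up to withdrawal are kept, and delivery data are taken from the hospital record unless the woman refuses their use. Randomised women are not replaced. Withdrawals are reported by arm and reason. A woman enrolled in error is excluded only on a criterion fixed before randomisation, judged without regard to arm.

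   State the same population in the Statistics section. For the few women randomised but never induced, fix the time origin in advance. Counting from randomisation is workable, at least as a sensitivity analysis; using it in the primary analysis would mix two origins.

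3. **Separate stopping the procedure from leaving the study.** Leave the clinical handling of a vasovagal attack as written, but treat it as the end of the procedure, with follow-up and analysis continuing. Reconcile this with the storage and safety-reporting sections.

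**Cost.** Mostly protocol wording, with a possible change to the information sheet and ethics review. Staff access to the medical record is already provided for (Ethical Issues, 2.e), but for checking conduct and data, so use of delivery data after withdrawal may need to be stated. The statistical price is slight dilution from women who did not receive, or did not complete, the assigned method.

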- j. In Group 2, transcervical Foley catheter No. 18 F will be inserted under aseptic technique into the endocervical canal surpassed beyond the internal os. The balloon will be inflated with 60 ml of sterile water and the catheter is plastered to patient's thigh with gentle traction. The catheter will be checked for its position and the traction at 6 hours interval. If it were expelled spontaneously, it would not be re-inserted. Otherwise, the catheter will be removed after 24 hours.
- k. Post-induction CTG will be performed at 1 hour after the first membrane sweeping in Group 1 and after transcervical Foley catheter insertion in Group 2.
- l. The uterine contractions, maternal temperature and fetal heart rate (via handheld Doppler device) will be monitored every 4 hours.
- m. After 24 hours, improvement of modified Bishop score will be assessed.
 - i. If the cervix is favourable for amniotomy, amniotomy will be performed followed by augmentation with intravenous oxytocin.

- ii. If the cervix is still unfavourable and amniotomy is impossible, membrane sweeping will be continued for one more day in Group 1 whereas conservative management will be undertaken for one day in Group 2. Suitability for amniotomy will be reassessed on the next day.
 - n. After amniotomy, subsequent intrapartum management will be based on the hospital protocol.
 - o. Oxytocin augmentation will be started when desired contractions are not achieved at 2 hours after amniotomy or labour progress falls below the action line of partogram.
 - p. Our oxytocin infusion regime begins with 2 mU/min. An increment in dosage is made every 30 minutes until desired contractions of 3-4 in 10 minutes lasting 45-60 seconds. The maximum oxytocin dose is 16 mU/min.
 - q. Continuous CTG monitoring will be undertaken throughout the labour process.
 - r. Oxytocin augmentation will not be started or will be withheld when there is non-reassuring fetal heart rate.
 - s. If amniotomy is still impossible after 2 days of IOL, the ward Obstetrician will discuss with women regarding option of Caesarean section.
6. Criteria for suspending or terminating the study:

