1. This study does not involve vulnerable subjects.

RESULTS (Dummy tables)**Table 1: Demographic characteristics**

Characteristics	Membrane sweeping	Transcervical Foley catheter	p-value
Age, years			
Parity			
Gestational age			
Ethnicity, n (%)			
Iban			
Melanau			
Bidayuh			
Malay			
Chinese			
Indian			
Others			
Foreigner			
Body mass index, kg/m ²			
Previous Caesarean section			
Tested scar			
Untested scar			
Indication of induction of labour			
Postdate			
Fetal growth restriction			
Hypertension			
Diabetes			
Others			

Table 2: Induction outcomes in two groups

Outcomes	Membrane sweeping	Transcervical Foley catheter	p-value
Bishop score at start of induction			
Bishop score after 24 hours of induction			
Bishop score after 48 hours of induction			
Change in Bishop score			
Oxytocin required			

Table 3: Delivery outcomes and maternal complications in two group

Outcomes	Membrane sweeping	Transcervical Foley catheter	p-value
Mode of delivery			
Vaginal			
Caesarean section			
Overall			
Induction to delivery interval			
Oxytocin augmentation duration			
Vaginal delivery			
Induction to delivery interval			
Amniotomy to delivery interval			
Oxytocin augmentation duration			

Within 24 hours of induction

Between 24-48 hours of induction

Indication for Caesarean section

Poor progress

Failed induction

Acute fetal distress

Suspected scar dehiscence

Others

Maternal complications

Uterine rupture

Uterine hyperstimulation

Post-partum haemorrhage

Maternal pyrexia

Duration of hospitalisation

Table 4: Neonatal outcomes in two groups

Outcomes	Membrane sweeping	Transcervical Foley catheter	p-value
APGAR score at 5 minutes			
Cord pH			
Birth weight			

[figure not shown]
REFERENCES

2. National Institute for Health and Clinical Excellence. *Inducing Labour*. NICE CG70. London: NICE; 2008.

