b) After 48 hours of induction

(only applicable to Foley group)

Achieved favourable Bishop (≥ 8) score: *(please tick)*

Yes

No

(if yes, proceed to sub-question;

if no, proceed to next question)

a) Interval to achieve favourable Bishop score

_____ (hours)

Achieved cervix allowing amniotomy: *(please tick)*

Yes

No

(if yes, proceed to sub-question;

if no, proceed to next section)

a) Bishop score at that time

b) Os dilatation at that time

_____ (cm)

c) Cervical length at that time

_____ (cm)

SECTION C: DELIVERY OUTCOMES

Oxytocin required during delivery (*please tick*) Yes No

Mode of delivery: (*please tick*)

- Vaginally Within 24 / 24-48 / > 48 hours of induction (*please circle*)
- Instrumentation Vacuum / forceps (*please circle*)
Indication: _____
- Caesarean section Indication: _____

Durations (regardless of final mode of delivery):

- a) Induction to delivery _____ (hours)
- b) Oxytocin augmentation _____ (minutes)

Durations (only for vaginal delivery including instrumental delivery):

- a) Induction to vaginal delivery _____ (hours)
- b) Amniotomy to vaginal delivery _____ (hours)
- c) Oxytocin augmentation _____ (minutes)

Estimated blood loss (EBL): ml

If EBL > 500ml, please mention cause: (*please tick*)

- a) Uterine atony
- b) Perineal trauma
- c) Retained placenta
- d) Coagulopathy
- e) Others *Please specify:*

Maternal complications: (*please tick*)

- a) Uterine rupture Yes No
- b) Uterine hyperstimulation Yes No
- c) Post-partum haemorrhage Yes No
- d) Maternal pyrexia Yes No

Neonatal outcomes:

- a) APGAR score at 5 minutes _____ To: NICU / SCN / mother (*please circle*)
- b) Cord pH _____
- c) Birth weight _____

SECTION D: MATERNAL SATISFACTION

If you had to repeat it all over again, would you take part in the study? (*please tick*)

Yes

No

If no, please provide reason(s). _____

Notes:

Uterine hyperstimulation : > 5 contractions per 10 minutes for at least 20 minutes or a contraction lasting at least 2 minutes with/without abnormal fetal heart rate

Post-partum haemorrhage : Estimated blood loss \geq 500 ml

Maternal pyrexia : Temperature >38.0 °C once, or 37.5 °C on two occasions 2 hours apart

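### The 48-hour Bishop score test compares women selected by their 24-hour response, and the readable plan does not say who contributes

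*Combined protocol and SAP*

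**What the plan says.** Objectives and Purpose 2.a.i asks for a between-arm comparison of Bishop score improvement at 24 h and at 48 h. Assessment of Efficacy 2.a.i repeats it as a secondary outcome, "Improvement of modified Bishop score at interval of 24 hours and 48 hours after induction", and names no population.

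Statistics 2 lists Bishop score among the numerical data and says: "Independent T-test (data with normal distribution) or Mann-Whitney U test (if data not normally distributed) will be used to compare these outcomes". Dummy Table 2 has a p-value column, a row "Bishop score after 48 hours of induction", and a row "Change in Bishop score" with no time point.

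Trial Design 5.m sets out care after the 24 h assessment. Item 5.m.i reads: "If the cervix is favourable for amniotomy, amniotomy will be performed followed by augmentation with intravenous oxytocin". For women still unfavourable, 5.m.ii says "membrane sweeping will be continued for one more day in Group 1 whereas conservative management will be undertaken for one day in Group 2", and then "Suitability for amniotomy will be reassessed on the next day".

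The data form (Appendix 3, Section B) has a line "After 48 hours of induction", with no instruction for women who have already had amniotomy. The only stated rule that removes data from analysis concerns withdrawn women (Selection and Withdrawal of Subjects, 6.b.ii).

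**The concern.** The 24 h assessment acts as a gate. Women who pass it leave the ripening phase, and only those who do not pass have a second day and a planned reassessment. No section says so outright, but it follows that a 48 h score reflecting ripening exists only for women who had not responded enough by 24 h. Whether a woman belongs to that group is settled after randomisation, by the response under study.

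The form's line would also allow a score to be taken from everyone at 48 h. But a score taken after amniotomy and oxytocin measures labour, and a woman already delivered has none. Neither reading gives a clean randomised comparison of ripening.

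At stake is the 48 h half of objective 2.a.i. An arm that ripens more women on day 1 takes its best responders out of its own 48 h mean, so its advantage would usually look smaller than it is. If the change row in Table 2 is taken to 48 h, the same selection applies to it.

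**Working it through.** The plan gives no figure to reproduce here, and the documents give no Bishop SD or ripening rate. Every input below is an assumption, used to show direction and range.

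**1. Raw score, equal day-2 gains.** Let the 24 h score be normal with mean m in the sweeping arm, mean m + d in the Foley arm, and common SD s. A woman contributes at 48 h only if her 24 h score is below a gate g. With z = (g − m)/s, the mean among contributors is m − s·φ(z)/Φ(z). A day-2 gain equal in both arms cancels. The amount removed is d minus the difference between the two contributor means.

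Grid: m = 4.0, 4.5, 5.0, 5.5; s = 1.5, 2, 2.5; g = 7 or 8. The two extremes for d = 1.0 are:

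| m, s, g | Sweeping contributors | Foley contributors | Apparent difference | Removed |
|---|---|---|---|---|
| 4.0, 1.5, 8 | 3.983 | 4.917 | 0.934 | 0.066 |
| 5.5, 2.5, 7 | 4.352 | 4.812 | 0.460 | 0.540 |

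For d = 0.5 the range removed is 0.02 to 0.26. For d = 1.5 it is 0.14 to 0.85.

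**2. A looser gate.** The protocol gates on suitability for amniotomy, not on a score. If that judgement correlates r with the score, the amounts are multiplied by r. For d = 1.0 this gives 0.05 to 0.43 at r = 0.8 (0.066 × 0.8; 0.540 × 0.8) and 0.03 to 0.22 at r = 0.4.

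**3. Raw score against improvement.** The listed outcome is improvement, while Statistics 2 names the score. The gate acts on the level reached, so part of the selection falls on baseline and cancels in a change from baseline. This was checked by simulation: baseline about N(4, 1.3), rounded and limited to 0–6; mean 24 h gain 2 in sweeping and 3 in Foley, SD about 1.4; mean day-2 gain 1 in both arms; gates 6, 7 and 8. The contributors are 50% v 30%, 70% v 50% and 86% v 70% (sweeping v Foley).

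- With gains on the two days independent, selection removes about 0.44 to 0.69 of a 1-point raw-score difference, but 0.23 to 0.36 of a 1-point improvement difference.
- If responsiveness is partly shared between days, a true improvement difference of 1.0 appears as 0.55, 0.62 and 0.71 at gates 6, 7 and 8, so 0.45, 0.38 and 0.29 are removed.

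**4. Unequal day-2 gains.** Day-2 care differs by arm, so equal gains cannot be taken for granted. Take m = 5.5, s = 2, g = 8 and d = 1.5, with a day-2 gain of 1 in sweeping and 0 in Foley. Over all women, the true 48 h difference is 1.5 − 1 = +0.5. Selection removes 0.610, so contributors show 1.5 − 0.610 − 1 = −0.11. The sign has changed.

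**5. When there is no bias.** With the same 24 h distribution in both arms, the same gate and equal day-2 gains, the simulated difference among contributors is 0. Equal proportions favourable are not enough. With means 6.75 and 7.25, SDs 2.5 and 1.5 and gate 8, 30.9% are favourable in each arm, yet an all-women difference of −0.50 becomes −1.01. That case lies outside the grid in step 1 and only shows that the proportions alone settle nothing.

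**The case against.** The strongest reply is that this is half of one secondary outcome, that every magnitude rests on assumed inputs, and that early benefit is already captured by the 24 h score, the primary interval and the vaginal delivery rates within 24 h and at 24–48 h. On this view it is enough to define the 48 h set, or to label the row descriptive, and replacing the test is a preference. The point about scope stands. The case for change rests on structure, since the selection follows from 5.m whatever the inputs. Labelling the row descriptive is part of the remedy, but alone it leaves the 48 h half of the objective without a randomised answer.

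It can also be said that the plan may define the 48 h group somewhere unreadable. The Appendix 1 flow chart is not shown, so the silence is established only for the readable text. On the form, a bracketed note limiting an item to the Foley group prints just after the 48 h line. A reader might infer that the 48 h score is collected in one arm only. The note more likely belongs to the catheter-dislodgement line and was displaced when the text was extracted, so no weight is placed on it.

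A third objection is that a proportion is coarser than a score and may lose power. That is probably true. No power figure is offered, because a credible one needs the variability of the day-2 gain, which the documents do not give.

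**Conclusion.** The concern holds for the 48 h Bishop score comparison. Among women with a ripening score at 48 h, the arms are no longer the randomised groups. The contrast is generally biased when the 24 h distributions differ, usually against the method that ripens more women by 24 h. On the assumed grid with equal day-2 gains, 0.07 to 0.54 of a true 1-point raw-score difference is lost. The loss on improvement was smaller than on the raw score in the illustration with independent gains. The actual size in this trial is unknown.

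Three stronger readings are not supported. A reader might infer that selection can only shrink the difference and never reverse it. That depends on equal day-2 gains, which the different day-2 care gives no reason to assume. A reader might carry the raw-score ranges straight over to improvement, but they describe a different variable. And a reader might extend the criticism to the primary outcome or the 24 h comparison. Neither passes through this gate, although some women may lack a 24 h score because they laboured or delivered first, which should be reported.

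**What to change.** - Do not test the 48 h score or the 48 h change between arms. Report both descriptively among women still unfavourable at 24 h, giving by arm the number contributing and the reasons for having no score. State the time point of the change row in Table 2.
- For the 48 h half of objective 2.a.i, compare the proportion of randomised women who reach a favourable cervix (score of 8 or more, or cervix allowing amniotomy) or deliver vaginally, by 24 h and by 48 h. Count Caesarean before that as not reached. Use the planned chi-square or Fisher test, with a risk difference and 95% CI.
- Keep the 24 h score comparison, and report by arm the women with no 24 h score because they laboured or delivered first.
- Add a time to the form's item on a cervix allowing amniotomy. The score-of-8 item already has an interval in hours, and vaginal delivery is already recorded by time band.

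The cost is SAP wording and one form entry, plus a decision on withdrawn women. Their data are to be destroyed (Selection and Withdrawal of Subjects, 6.b.ii), and a vasovagal attack after sweeping leads to withdrawal (Assessment of Safety, 4.b.ii), a loss confined to one arm. All randomised women can be counted only if withdrawn women's data are retained with their agreement. Otherwise the denominator is women not withdrawn, and withdrawals should be counted by arm. The remaining downsides are a coarser endpoint, probably with less power than a score test, and an unblinded judgement of suitability for amniotomy.
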